10.8 Adverse Event Reporting Requirements

10.8.1 Reporting to Sponsor

Not applicable

10.8.2 Reporting to IRB

The investigator or designee will report events to the FHCRC IRB in accordance with the policies of the IRB.

10.8.3 Institution-Sponsored IND Reporting Requirements

Not applicable

10.8.4 Study Coordinating Center Requirements

Not applicable

10.8.5 FDA Reporting Requirements

Not applicable

11.0 DATA AND SAFETY MONITORING PLAN

Institutional support of trial monitoring will be in accordance with the FHCRC/University of Washington Cancer Consortium Institutional Data and Safety Monitoring Plan. Under the provisions of this plan, FHCRC Clinical Research Support (CRS) coordinates data and compliance monitoring conducted by consultants, contract research organizations, or FHCRC employees unaffiliated with the conduct of the study. Independent monitoring visits occur at specified intervals determined by the assessed risk level of the study and the findings of previous visits per the institutional DSMP.

In addition, protocols are reviewed at least annually and as needed by the Consortium Data and Safety Monitoring Committee (DSMC), FHCRC Scientific Review Committee (SRC) and the FHCRC/University of Washington Cancer Consortium Institutional Review Board (IRB). The review committees evaluate accrual, adverse events, stopping rules, and adherence to the applicable data and safety monitoring plan for studies actively enrolling or treating subjects. The IRB reviews the study progress and safety information to assess continued acceptability of the risk-benefit ratio for human subjects. Approval of committees as applicable is necessary to continue the study.

The trial will comply with the standard guidelines set forth by these regulatory committees and other institutional, state and federal guidelines.

12.0 DATA MANAGEMENT/CONFIDENTIALITY

The investigator will ensure that data collected conform to all established guidelines. Each subject is assigned a unique subject number to protect subject confidentiality. Subjects will not be referred to by this number, by name, or by any other individual identifier in any publication or external presentation. The licensed medical records department, affiliated with the institution where the subject receives medical care, maintains all original inpatient and outpatient chart documents.

All participants' identifying information is kept in restricted access, password-protected files; only authorized persons have access to confidential data. Investigators and lab personnel will not have access to any identifying information. Only study-assigned ID number labels are placed on biospecimen aliquots and all data files with participant information contain only a study-assigned ID number, but no names. No data will be published or released in a way in which individuals could be identified. Any data that is shared with other investigators will be stripped of any identifiers.

13.0 STATISTICAL CONSIDERATIONS

13.1 Study Design

Individuals with stage II-IV ovarian cancer (N=98) who have completed primary treatment within one to six months and are in clinical remission will be randomized to a 24-week home-based exercise program or wait-list control. The exercise prescription will consist of 150 minutes of moderate aerobic exercise (the equivalent of brisk walking or higher intensity) per week, with weekly telephone-based support by an exercise physiologist. The control group will continue their usual activities and will be offered the exercise intervention after 24 weeks. Baseline and 24-week assessments will include validated questionnaires assessing distress and health-related quality of life, serum levels of IL-6 and VEGF, salivary cortisol levels measured at bedtime for three consecutive days, and 24-hour urinary norepinephrine levels. Participants will also complete the questionnaires at 12 weeks to provide additional longitudinal data. Compliance to the intervention will be assessed by daily activity logs, actigraphs, and completion of weekly telephone calls.

13.2 Primary/Secondary Endpoints/Hypotheses and Analytical Methods

Descriptive statistics will be performed for baseline data, and distributions of outcome measures will be characterized using scatterplots, histograms, and summary statistics (e.g., mean, median, standard deviation, quartiles, range) to identify extreme outliers. Outcome variables will be log-transformed if their distributions are not symmetric. We will also examine if these measurements are balanced between the study intervention groups. The primary assessment of the exercise intervention effects will compare the average change from baseline to 24-week follow-up outcome measures (such as SF-36 physical component score) between the exercise group and the control group. Analyses will be intention-to-treat. The generalized estimating equations (GEE) modification of linear regression will be used in order to model the relationship between the outcome measures and exercise intervention and to account for the correlation within individual data over time. The GEE model will adjust for the measurement time and other potential covariates. Prior to fitting the GEE model, logarithmic transformation will be applied (if appropriate) to the outcome data to achieve approximate normality and variance stabilization. Our statistical inference on each outcome will use the standard large-sample approximation, namely, two-sided Z-test and Z-confidence intervals based on the limiting Gaussian distribution. More specifically, for the primary comparison between exercise group *vs.* control group, let Y_{ij} be the outcome measure (or log-transformed if appropriate) of interest for participant i at time j , where j is 0 for baseline and 1 for 24 week follow-up, X_i be the indicator variable for the intervention status (1=intervention, 0=control) and Z_i represent a vector of other potential adjusting variables (such as age, BMI). The linear model is as follows:

$$E[Y_{ij}] = \alpha_0 + \alpha_1 j + \beta_0 X_i + \beta_1 X_i j + \gamma^T Z_i, \text{Var}[Y_{ij}] = \sigma^2 \text{ and } \text{Cov}[Y_{ij}, Y_{kl}] = \rho \text{ if } i = k \text{ and } j \neq l, \text{ and } 0 \text{ otherwise.}$$

The parameter β_1 is of our main interest and represents the mean difference in the outcome change from baseline to follow-up between participants in the exercise group and participants in the control group, adjusting for covariates Z such as age and BMI. We will first assess β_1 without any adjustments for Z (unadjusted analysis), and then add Z (adjusted analysis). Under the null hypothesis of no difference between intervention and control on the changes in the outcome measure, β_1 is equal to zero. If the exercise intervention indeed results in a greater reduction/increase in the outcome measure of interest in the exercise group compared with the control group, then β_1 is different from zero. Our statistical inference on β_1 will use the standard large-sample approximation, namely, two-sided Z-test and Z-confidence intervals based on the limiting Gaussian distribution.

Our analysis will be based primarily on intention-to-treat principle, but with minor modifications for practical considerations. The principles of ITT analyses are (i) keep participants in the intervention groups to which they were randomized, regardless of the intervention they actually received; (ii) measure outcome data on all participants; and (iii) include all randomized participants in the analysis (107). However, if data of individuals are lost, or are unavailable for other reasons immediately after randomization, then we will not include these individuals in the analysis (modified intention-to-treat). Under the modified intention-to-treat principle, enrolled participants who were later found to be ineligible will not be included in the primary analysis. To take adherence into account, we will also perform per-protocol analysis which includes only individuals who are considered adherent to the intervention assignment. Per-protocol analysis will not be our primary analysis, and we will report in detail the criteria for exclusion of individuals.

If we encounter missing data due to drop out or assay issues, we will apply mixed model regression using the available data in the analysis. In general, our analysis based on available data will be similar to the analysis using the individuals who do not have missing data (complete-case analysis) if the missing data mechanism is completely at random (108). When the

Protocol 10045

missing data mechanism is at random (MAR), regression imputation and weighted using inverse selection probability are in general the same (109). Hence, under MAR we plan to perform regression imputation or multiple imputation in the analysis. However, missing data may be informative with a nonignorable missing (NIM) mechanism in the sense that the missing data mechanism may be related to the unobserved missing data. When the data may be NIM, we will consider weighted estimation (110), and sensitivity analysis under different assumptions about the missing data. The sensitivity analysis will include, but not restricted to, approaches under the last observation carry forward. We will also apply pattern mixture models for sensitivity analysis to address informative missing data. We will examine the missing data mechanism, and investigate if the regression association among individuals with and without missing data, respectively.

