We (PI: [name]) recently completed a randomized controlled trial of 144 physically inactive ovarian cancer survivors, randomized to six months of home-based, moderate-intensity exercise vs. control (17). At baseline, participants were on average 1.7 years post-diagnosis and exercised 31 minutes per week; 55% had advanced stage (III-IV). Intervention arm participants exercised a mean of 166 minutes per week of moderate exercise; 65% reported adhering to the goal of \geq 150 minutes per week, and 84% reported \geq 120 minutes per week (80% of goal). 83% of participants with stage III-IV ovarian cancer exercised at least 80% of goal, compared to 75% of participants with stage I-II ($p=0.41$), demonstrating that individuals with advanced-stage ovarian cancer can also exercise. Ovarian cancer survivors are highly motivated to adhere

Protocol 10045

to an exercise program and can exercise at recommended levels. Individuals in the exercise arm improved physical health-related quality of life, compared to a decreased physical health-related quality of life in control arm (mean 36-item Short Form Health Survey- Physical Component Score change of 1.8 ± 1.1 vs. -2.0 ± 1.2 , $P = 0.02$). A weakness of this study is that it relied on self-report for exercise adherence. We include actigraphy as an objective measure in our proposed study.

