9.0 SUBJECT DISCONTINUATION FROM STUDY

Subjects may be removed from this study at any time at their discretion. Subjects may also be removed from this protocol if they develop any untoward side effects from the study intervention.

Cancer recurrence does not mandate study discontinuation. If a subject develops cancer recurrence, they may still continue on the study if they are willing and able. Exercise is safe for individuals with cancer who are undergoing active treatments including chemotherapy. The exercise physiologist may alter their exercise prescription as needed based on the individual's functional ability and medical condition. If a participant desires to discontinue the study, she may discontinue the study at any time. If an individual desires to stop exercising but is willing to complete study assessments, she will complete originally planned study assessments (including clinic visit) at the originally specified time points.

An explanation for discontinuing the study is recorded for each subject discontinuing the study on the appropriate CRF/eCRF. Treatment in this study must be discontinued for any of the following reasons:

- if the PI decides to stop the study;
- at Investigator's discretion;
- at the subject's request;
- Grade 4 or life-threatening toxicity (See Section 11, Adverse Events) attributable to study intervention

Target enrollment is 98 participants, accounting for up to 20% drop-out. Power calculations are based on 78 participants. Additional subjects may be enrolled in the study to replace individuals who have dropped out in order to achieve the goal of 78 participants completing the study.

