13.3 Sample Size and Power

98 individuals will be randomized. Accounting for up to 20% drop-out, power calculations are based on 78 participants.

Table 1. Minimum detectable absolute difference in mean change from baseline to 24 weeks between two groups (n=39 for Control group and n=39 for Exercise group) for the study endpoints, given an intra-individual correlation (ρ) of 0.5, 0.65 or 0.8, at 80% power, and adjusting for the number of hypotheses tests with 7 primary endpoints (type I error of 0.05/7).

Endpoint	Mean	SD	Minimum detectable absolute difference (% change)		
			$\rho = 0.5$	$\rho = 0.65$	$\rho = 0.8$
Distress (Perceived Stress Scale) ^a	19.23	6.77	5.41 (28.16%)	4.53 (23.56%)	3.42 (17.81%)
Distress (Hospital Anxiety and Depression Scale-anxiety subscale) ^b	7.4	3.9	3.12 (42.15%)	2.61 (35.27%)	1.97 (26.66%)
Distress (Hospital Anxiety and Depression Scale-depression subscale) ^b	5.8	3.5	2.87 (48.26%)	2.346 (40.4%)	1.77 (30.52%)
Quality of Life (36-item Short Form Survey- Physical Component Score) ^c	45.6	9.2	7.36 (16.14%)	6.16 (13.5%)	4.65 (10.21%)
IL-6 (pg/mL) ^d	2	0.7	0.56 (27.99%)	0.47(23.42%)	0.35 (17.70%)
VEGF (pg/mL) ^e	192	158.2	126.5 (65.88%)	105.8 (55.12%)	80(41.67%)
Salivary cortisol (nmol/L) ^d	4	0.6	0.48 (12.0%)	0.4 (10.04%)	0.3 (7.59%)

Mean and SD obtained from: ^a Perceived Stress Scale score in ovarian cancer survivors at the end of primary chemotherapy (111), ^b Hospital Anxiety and Depression Scale anxiety and depression subscale scores in ovarian cancer survivors towards end of primary chemotherapy (112), ^c 36-item Short Form Survey- Physical Component Score in our randomized controlled trial of exercise in ovarian cancer survivors (17), ^d biomarker levels in ovarian cancer survivors 6 months after primary treatment(113), and ^e VEGF levels in ovarian cancer survivors after completion of primary chemotherapy (114).

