13.4 Randomization

After baseline assessments are complete, participants will be randomized with equal probability to the exercise intervention (N=49) or wait-list control (N=49). Randomization will be blocked on stage (stages II-IIIA vs. IIIB-IV) and body mass index (<30 kg/m² vs. \geq 30 kg/m²) and will use permuted blocks with random size.

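### Normal-reference (Z) inference at 39 per arm is slightly liberal at 0.05/7 (about 0.0088 against 0.0071), and Section 13.2 names no test level, variance estimator or small-sample correction

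*Combined protocol and SAP*

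**What the plan says.** Section 13.2 models each outcome by GEE linear regression and bases inference on "two-sided Z-test and Z-confidence intervals based on the limiting Gaussian distribution". It repeats this for the treatment-by-time coefficient, for which inference "will use the standard large-sample approximation, namely, two-sided Z-test and Z-confidence intervals". It names no variance estimator (model-based or sandwich), degrees of freedom or small-sample correction. When data are missing through drop-out or assay problems, the same section changes the model: "we will apply mixed model regression using the available data in the analysis".

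The test level appears only in Section 13.3, in the caption of Table 1: "adjusting for the number of hypotheses tests with 7 primary endpoints (type I error of 0.05/7". Section 13.2 gives neither a level nor a multiplicity rule.

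On numbers, Section 13.3 says "Accounting for up to 20% drop-out, power calculations are based on 78 participants", that is 39 per arm. Section 13.4 has participants "randomized with equal probability to the exercise intervention (N=49) or wait-list control (N=49" per arm. Section 9.0 allows further enrolment "to replace individuals who have dropped out in order to achieve the goal of 78 participants completing the study".

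**The concern.** A normal reference treats the standard error as known. With 78 completers it is estimated on about 76 degrees of freedom. The mismatch is small at an ordinary 0.05 level, where the true size would be 0.0537. It grows in relative terms further into the tail, and 0.05/7 is well into the tail. An uncorrected sandwich variance, which 13.2 does not rule out, adds to it.

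Three things are at stake:

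- P-values and intervals come out slightly too optimistic. A statistic between 2.690 and 2.765 would be declared significant when an accurate test would not support it.
- The 80% power in Table 1 belongs to a test that does not quite hold its level.
- With seven primary endpoints and no level written in the analysis section, the 0.05/7 commitment could be disputed once results are seen.

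**Working it through.** **Inputs.** Two-sided level 0.05/7 = 0.00714, power 80%, 39 per arm, rho 0.5, 0.65 or 0.8, and the SDs (Table 1). Randomised per arm: 49 (13.4). Reference distribution: normal (13.2).

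**1. Reproduce Table 1.** z(1 − 0.05/14) = 2.690 and z(0.80) = 0.842, sum 3.532. The SD of change is SD·sqrt(2(1 − rho)), so

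difference = 3.532 · SD · sqrt(4(1 − rho)/39).

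- Perceived Stress Scale, rho 0.5: 3.532 × 6.77 × sqrt(2/39) = 5.41, as printed.
- SF-36 PCS, rho 0.65: 3.532 × 9.2 × sqrt(1.4/39) = 6.16, as printed.

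Twenty of the 21 cells agree apart from immaterial last-digit differences, so Table 1 rests on the normal approximation. The exception is HADS depression at rho 0.5, printed as 2.87 with 48.26%. The formula gives 2.80, and 0.4826 × 5.8 = 2.80, whereas 2.87/5.8 = 49.5%. The cell contradicts its own percentage.

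**2. True size of the Z test.** With normal data and a model-based variance, the completers' statistic follows t with 76 df (2 × 39 − 2).

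- t cut-off at 0.05/7: 2.765, against 2.690 for Z.
- Size of Z: 2·P(t76 > 2.690) = 0.0088.
- Uncorrected sandwich (variance too small by 38/39): 2·P(t76 > 2.690·sqrt(38/39)) = 0.0096.
- Uncorrected sandwich with a t cut-off: 0.0079. A t reference alone is therefore not enough in that case.
- All 98 followed (96 df), Z: 0.0084. More completers shrink the excess but do not remove it.

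**3. Power at the Table 1 differences, completers only.** Noncentral t, 76 df, noncentrality 3.532: 79.7% with the Z cut-off and 77.6% with the t cut-off. For 80% with t the differences must rise by 2.4%.

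**4. The available-data model.** Take 49 baselines and 39 follow-ups per arm, missing completely at random. The variance of the effect relative to completers only is

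[(1 + rho) + (1 − rho)·39/49]/2.

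| | rho 0.5 | rho 0.65 | rho 0.8 |
|---|---|---|---|
| Variance ratio | 0.949 | 0.964 | 0.980 |
| t76 power, formula | 80.2% | 79.4% | 78.6% |
| t76 power, simulated | 79.9% | 79.5% | 78.5% |
| Z power, simulated | 81.9% | 81.5% | 80.6% |
| Z size, simulated | 0.0087 | 0.0091 | 0.0086 |
| t76 size, simulated | 0.0071 | 0.0074 | 0.0070 |
| Change in difference for 80% with t | −0.2% | +0.6% | +1.4% |
| PCS difference for 80% with t | 7.34 | 6.19 | 4.72 |

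The simulation fits a REML compound-symmetry model to normal data, with 300,000 null trials (Monte Carlo SE 0.00017) and 80,000 effect trials per rho. A second simulation with 400,000 null trials per rho gave Z sizes of 0.0085 to 0.0087. The extra baselines recover power but do not correct the size.

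**5. Familywise error over seven tests at 0.05/7.** The documents give no correlation between endpoints, so an equal correlation is assumed and varied.

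| Assumed correlation | Z, model-based | Z, uncorrected sandwich |
|---|---|---|
| 0 | 6.0% | 6.6% |
| 0.3 | 5.6% | 6.2% |
| 0.5 | 5.0% | 5.4% |
| 0.7 | 3.9% | 4.3% |

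**The case against.** The strongest reply is that this hardly matters. The cut-off moves by 2.8%. The plan openly calls its method a large-sample approximation and uses it consistently in 13.2 and Table 1. The distress scales are likely to be correlated, and at a correlation of 0.5 or more Bonferroni's slack absorbs most or all of the excess. Under the planned available-data model, t-based power is within 1.4 points of 80%. The figure of 39 per arm is a planning floor, since drop-out is up to 20% and replacement is allowed; with 41 completers per arm, t-based power is 80.2%. Bonferroni at 0.05/7 is valid, so Holm is an option and not a correction.

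Most of this stands, and it limits the point to a minor one. It does not remove it. The per-test p-values and intervals are too optimistic whatever the correlation between endpoints, and the size of Z remains 0.0084 with complete follow-up. The protection from correlation is assumed, not documented. Holm is indeed a separate improvement that does not repair the Z reference.

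Two further objections shape the fix. A t reference alone fails with a raw sandwich, so the variance must be corrected too. And 13.2 offers GEE or a mixed model, unadjusted then adjusted, without saying which supplies the decision.

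**Conclusion.** The concern holds. At 39 completers per arm the planned Z test runs at about 0.0088 per endpoint (up to 0.0096 with an uncorrected sandwich) against the intended 0.0071. A properly referenced test has 77.6% power at the Table 1 differences for completers only, or 78.6% to 80.2% for the available-data model. This is a small-sample inaccuracy, not a design flaw. It should be corrected because only wording is needed, and because 13.2 also lacks the test level.

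The figures assume normal outcomes, and 76 df. The 0.0088 and the statement that t holds 0.05/7 require a model-based or corrected variance. The available-data figures also assume exactly 49 baselines and 39 follow-ups per arm, missing completely at random. Skewed biomarkers left untransformed could change them.

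**What to change.** In Section 13.2:

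1. Replace the Z reference by a small-sample-corrected GEE variance (for example Kauermann-Carroll) with a t reference, 76 df at 39 per arm; or by Kenward-Roger where the mixed model is used. For complete data, equal arms and no covariates, the Kauermann-Carroll factor is 39/38, which returns the ordinary two-sample t test on change. Its behaviour with incomplete data was not simulated here.
2. Name one model, and state whether the unadjusted or adjusted fit is decisive, so that each endpoint has one p-value.
3. Write the multiplicity rule: Holm step-down over the seven primary endpoints at two-sided familywise 0.05 on those p-values, with t-based intervals at the 0.05/7 level beside them. Holm never rejects fewer hypotheses than fixed 0.05/7. If the sponsor prefers Bonferroni, state 0.05/7 as the decision rule.

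In Table 1: label the differences as completers-only with 77.6% power under t, or raise them by 2.4%; optionally add 80.2%, 79.4% and 78.6% for the available-data model under missing completely at random. On the current Z basis, correct the HADS depression cell at rho 0.5 to 2.80.

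**Cost.** SAP wording and standard software options, with no new data or participants. Moving from Z to t gives up about two points of power (79.7% to 77.6% for completers only; 81.9%, 81.5% and 80.6% to 79.9%, 79.5% and 78.5% on available data, simulated).

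Holm's gain per endpoint over fixed 0.05/7 (both with t, completers only, assumed correlations 0 to 0.7) depends on how many endpoints have effects of Table 1 size: 0 to 0.1 point for one, 2.2 to 2.7 for three, 9 to 13 for seven. It is smaller for smaller effects. The earlier trial in Section 2.3 reports a "Physical Component Score change of 1.8 ± 1.1 vs. -2.0 ± 1.2", a difference of 1.8 − (−2.0) = 3.8, which is 62% of the 6.16 at rho 0.65. At that relative size power is about 29%, and Holm adds 1 to 2 points with three effects or 5 to 7 with seven. Holm decisions can also differ from the 0.05/7 intervals, which the text should acknowledge.

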7.7 End of Treatment (EOT) Visit Schedule and Procedures

Subjects who discontinue from the study will not require a clinic visit. They may continue their usual clinical care with their treating physicians. The reason for study discontinuation will be recorded. Participants who desire to stop exercising will be asked whether or not they are willing to complete study assessments. If they are willing, they will complete originally planned study assessments (including clinic visit) at the originally specified time points.

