Questionnaires (Appendix D) – all questionnaires will be completed at baseline, 12, and 24 weeks, unless specifically noted. Questionnaires may be completed online through REDCap, or on paper. Paper questionnaires may be mailed with a provided self-addressed stamped envelope or brought to clinic if participant opts for clinic visits.

Protocol 10045

- **Demographics, health history, and habits** (Demographics and health history at baseline only): Information will be collected on demographics, medical history, and health habits including medication use, tobacco use, and use of complementary and alternative therapies via a questionnaire.
- **7-day Physical Activity Log:** Participants will complete a seven-day Physical Activity Log (for the preceding 7 days) at baseline (before randomization) and 24-week assessments. Physical Activity Logs of exercise during the seven days preceding the assessment point will be used to determine minutes per week of moderate physical activity.
- Assessment of physical activity prior to ovarian cancer diagnosis (baseline only): Questions 6-8 of Form 34 v2: Personal Habits Questionnaire used by the Women's Health Initiative (https://www.whi.org/researchers/studydoc_layouts/15/WopiFrame.aspx?sourcedoc=/researchers/studydoc/WHI%20Forms/F034%20v2.pdf&action=default) will be included to assess the participant's estimated level of physical activity in the 2 years prior to their diagnosis of ovarian cancer.
- **Perceived Stress Scale (82):** This instrument uses a Likert-type rating scale to measure the degree to which situations in life are perceived as stressful, specifically unpredictable, uncontrollable, and overloading. The scale has excellent psychometric properties and relates to relevant outcomes in expected ways. Internal consistency is high with Chronbach's alpha's ranging from 0.75 to 0.86.
- **Hospital Anxiety and Depression Scale, anxiety and depression (HADS-A and HADS-D) subscales (83, 84):** This instrument is a well validated and widely used assessment of anxiety and depression. The 14-item scale has two subscales, anxiety and depression, derived from 7 questions each. Participant responses are scored on a scale of 0 to 3 with variable anchors (85). The Internal reliability is high with Chronbach's alpha for the anxiety scale ranging from 0.89-0.93 and 0.86-0.90 for the depression scale (83, 84).

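### Four of the seven primary endpoints are also scored at week 12, but the written primary model has no place for that visit and the drop-out methods do not say whether it is used

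*Combined protocol and SAP*

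**What the plan says.** Section 8.1 sets the questionnaire schedule: "all questionnaires will be completed at baseline, 12, and 24 weeks, unless specifically noted". None of the four questionnaire endpoints carries an exception, and the study calendar in Appendix C ticks week 12 for both arms. Section 13.1 repeats the schedule and gives its purpose: "Participants will also complete the questionnaires at 12 weeks to provide additional longitudinal data". IL-6, VEGF and salivary cortisol are taken only at baseline and 24 weeks.

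Section 13.2 says that the primary assessment "will compare the average change from baseline to 24-week follow-up outcome measures" between the arms. It then writes one linear model for all outcomes, with time coded "where j is 0 for baseline and 1 for 24 week follow-up", a single time slope, a single arm-by-time term β1, one variance and one within-person covariance. For data missing through drop-out or assay problems it adds "we will apply mixed model regression using the available data in the analysis". After that come regression or multiple imputation under missing at random (MAR), weighted estimation, last observation carried forward (LOCF) and pattern-mixture models. No variables are listed for the imputation, and week 12 is not mentioned in any of these methods.

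Section 7.7 says "Subjects who discontinue from the study will not require a clinic visit". The same section, and section 9.0, ask participants who stop exercising whether they will still complete the planned assessments.

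**The concern.** For a participant who leaves the study altogether after week 12, that questionnaire is the last record of how she was doing. If outcomes exist only at j = 0 and j = 1, the natural reading of the available data is the available baseline and 24-week values, so she contributes her baseline and nothing else.

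MAR is conditional on what the model contains. If leaving depends on the week-12 score, the data can be MAR in a model that includes that score and not MAR in one that omits it. Unweighted GEE, the named primary method, generally needs the stronger condition of missing completely at random. Only the exercise arm has the programme and weekly calls during the 24 weeks, so drop-out that differs by arm is plausible.

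There is also a pre-specification issue. Two or three visits is a real analytic choice for four primary endpoints, and the plan leaves it open.

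**Working it through.** **1. Inputs from the plan (sections 13.3 and 13.4).** 98 randomised, 49 per arm; up to 20% drop-out, so 39 completers and 10 lost per arm; seven primary endpoints at 0.05/7, two-sided; 80% power; correlation ρ of 0.5, 0.65 or 0.8; PCS SD 9.2.

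**2. The plan's own figures.** 78/(1 − 0.20) = 97.5, rounded up to 98. The minimum detectable difference (MDD) for PCS is (z₁₋α/₂ + z₀.₈₀) × SD × √(2(1 − ρ)) × √(2/39), with 2.690 + 0.842 = 3.532. At ρ = 0.5 this is 3.532 × 9.2 × 1 × 0.2265 = 7.36. At 0.65 and 0.8 it is 6.16 and 4.65. All three match Table 1, which therefore rests on a two-point change score in completers and uses no week-12 information.

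**3. Precision.** A two-visit model that keeps all 49 baselines has per-arm variance of change, in SD² units, (1 − ρ)²/49 + (1 − ρ²)/39. At ρ = 0.5 this is 0.00510 + 0.01923 = 0.02433, so the PCS MDD is 3.532 × 9.2 × √(2 × 0.02433) = 7.17. At 0.65 and 0.8 it is 6.05 and 4.61.

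I then added week 12 by generalised least squares, with L of the 10 lost per arm leaving after week 12. L is an assumption.
- One common ρ across visits, L = 10: the MDD is 7.10 / 5.96 / 4.52, and power rises by at most 1.8 points.
- Adjacent-visit correlations of 0.65–0.88, L = 5 to 10: the ratio of standard errors is 0.964–0.989, a reduction of about 1–4%.

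**4. Bias by simulation.** Assumptions, none of them in the documents: no true effect; late drop-out in the exercise arm only, depending only on the week-12 score. *Graded* means an odds ratio of 2.7 per SD worse at week 12. *Worst* means that all the lowest scorers leave. The two-visit model keeps every baseline. Entries are bias in SD units, with Monte Carlo error of about 0.002.

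| ρ 0–24 / adjacent | 10% graded | 10% worst | 20% graded | 20% worst |
|---|---|---|---|---|
| 0.5 / 0.65 | 0.029 | 0.071 | 0.059 | 0.136 |
| 0.65 / 0.75 | 0.026 | 0.062 | 0.049 | 0.121 |
| 0.8 / 0.88 | 0.017 | 0.044 | 0.033 | 0.091 |
| 0.8 / 0.8 | 0.015 | 0.038 | 0.030 | 0.077 |

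The three-visit bias is zero to within 0.002 SD throughout. Multiplying by 9.2: at 10%, 0.015 × 9.2 = 0.14 up to 0.071 × 9.2 = 0.65 points; at 20%, 0.030 × 9.2 = 0.28 up to 0.136 × 9.2 = 1.25 points (1.3 to one decimal). The direction favours exercise.

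**5. Hand check.** With a common ρ, the coefficient of week 12 on week 24 given baseline is ρ/(1 + ρ). If L late drop-outs in one arm score d SD worse at week 12 than completers with the same baseline, the bias is (L/49) × ρ/(1 + ρ) × d × 9.2.
- L = 2, ρ = 0.5, d = 0.5: 0.0408 × 0.333 × 0.5 × 9.2 = 0.06 points.
- L = 5, ρ = 0.65, d = 1: 0.102 × 0.394 × 9.2 = 0.37 points.
- L = 10, ρ = 0.8, d = 1: 0.204 × 0.444 × 9.2 = 0.83 points.

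This is the same order as the simulation.

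**6. Scale.** The standard error of the two-visit PCS contrast is 7.17/3.532 = 2.03 at ρ = 0.5 and 4.61/3.532 = 1.31 at ρ = 0.8. The 10% cases come to about 0.1–0.3 of a standard error, and the worst 20% case to about 0.6.

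**The case against.** A reader might infer that the plan throws the week-12 scores away. The text does not go that far. The two-time notation is introduced for the primary comparison. The drop-out methods are stated without restricting visits, imputation could include week 12, and LOCF would naturally carry it forward. What stands is that week 12 is absent from the written primary model and its use elsewhere is unspecified. LOCF does not fill the gap, because it is only a sensitivity analysis and assumes no change after the last visit.

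A reader might also infer from section 7.7 that anyone leaving after week 12 provides no 24-week data. That section waives only a clinic visit, and these four endpoints are questionnaires that can be completed online or on paper by mail. Participants who stop exercising are asked to stay for assessments, and under section 9.0 recurrence does not force withdrawal. The point is therefore limited to full withdrawals between weeks 12 and 24, for which the documents give no number.

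The sizes rest on stacked assumptions. The 20% case puts the whole drop-out allowance for the exercise arm after week 12, and its top figure needs every lowest scorer to leave. The figures also apply to a model that keeps every baseline. With equal adjacent correlations, the expected change given the week-12 score is (ρ₁₂,₂₄ − ρ₀,₁₂) × Y₁₂ = 0 in SD units, so a completers-only change score would escape this particular bias. It would do so only under that equality, and by leaving out randomised participants.

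**Conclusion.** The point holds as a gap in specification with a modest possible bias. Four of seven primary endpoints have a mid-study score that the written primary model cannot use, and no fallback gives that score a role. Under one-arm late drop-out driven by the week-12 score, with ρ of 0.5–0.8, the two-visit bias is about 0.02–0.07 SD (0.1–0.7 PCS points) at 10% and 0.03–0.14 SD (0.3–1.3 points) at 20%. Against the 3.8-point PCS difference in the earlier exercise trial described in section 2.3 (1.8 versus −2.0), only the upper end would noticeably colour the result. Similar drop-out in both arms would largely cancel it.

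The case rests on validity and pre-specification; the precision gain alone would not justify a change. It would be wrong to read the zero three-visit bias as general protection. It follows from letting drop-out depend only on the observed week-12 score, and withdrawal caused by deterioration after week 12 would still bias a three-visit model. This is a cheap improvement, not a flaw that undermines the trial.

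**What to change.** In section 13.2, for the Perceived Stress Scale, HADS anxiety, HADS depression and SF-36 PCS, state a mixed model with three visits (0, 12 and 24 weeks), visit as a categorical factor, arm-by-visit terms and unstructured covariance. Define β1 as the 24-week arm-by-visit contrast. State that any imputation model for these endpoints includes the week-12 score. Leave the three biomarkers at two visits, and keep the planned pattern-mixture analysis for withdrawal related to events after week 12.

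The cost is a sentence or two of text, settled before outcomes are compared by arm. The endpoints, the 24-week comparison, the 0.05/7 level and the data collection do not change. The statistical price is a few more covariance parameters: six for three unstructured visits, against the single variance and single covariance now written, which is workable with 78 to 98 participants.
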